6.2 Nonserious Adverse Events

A *nonserious adverse event* is an AE not classified as serious.

6.2.1 Nonserious Adverse Event Collection and Reporting

The collection of nonserious AE information should begin at initiation of study drug. Nonserious AE information should also be collected from the start of a placebo lead-in period or other observational period intended to establish a baseline status for the subjects.

Nonserious AEs should be followed to resolution or stabilization, or reported as SAEs if they become serious (see [Section 6.1.1](#)). Follow-up is also required for nonserious AEs that cause interruption or discontinuation of study drug and for those present at the end of study treatment as appropriate. All identified nonserious AEs must be recorded and described on the nonserious AE page of the CRF (paper or electronic).

All nonserious AEs (not only those deemed to be treatment-related) should be collected continuously during the treatment period and for a minimum of 100 days following the last dose of study treatment.

Completion of supplemental CRFs may be requested for AEs and/or laboratory abnormalities that are reported/identified during the course of the study.

6.3 Laboratory Test Result Abnormalities

The following laboratory test result abnormalities should be captured on the nonserious AE CRF page or SAE Report Form (paper or electronic) as appropriate:

- Any laboratory test result that is clinically significant or meets the definition of an SAE
- Any laboratory test result abnormality that required the subject to have study drug discontinued or interrupted
- Any laboratory test result abnormality that required the subject to receive specific corrective therapy.

It is expected that wherever possible, the clinical rather than laboratory term would be used by the reporting investigator (eg, anemia versus low hemoglobin value).

6.4 Pregnancy

If, following initiation of the study drug, it is subsequently discovered that a study subject is pregnant or may have been pregnant at the time of study exposure, including during at least 5 half lives after product administration, the investigator must immediately notify the BMS Medical Monitor/designee of this event and complete and forward a Pregnancy Surveillance Form to BMS Designee within 24 hours of awareness of the event and in accordance with SAE reporting procedures described in [Section 6.1.1](#).

In most cases, the study drug will be permanently discontinued in an appropriate manner (eg, dose tapering if necessary for subject safety).

In the rare event that the benefit of continuing study drug is thought to outweigh the risk, after consultation with BMS, the pregnant subject may continue study drug after a thorough discussion of benefits and risk with the subject

The investigator must immediately notify the BMS (or designee) Medical Monitor of this event and complete and forward a Pregnancy Surveillance Form to BMS (or designee) within 24 hours of awareness of the event and in accordance with SAE reporting procedures described in [Section 6.1.1](#).

Follow-up information regarding the course of the pregnancy, including perinatal and neonatal outcome and, where applicable, offspring information must be reported on the Pregnancy Surveillance Form.

Any pregnancy that occurs in a female partner of a male study participant should be reported to BMS. Information on this pregnancy will be collected on the Pregnancy Surveillance Form.

6.5 Overdose

An overdose is defined as the accidental or intentional administration of any dose of a product that is considered both excessive and medically important. All occurrences of overdose must be reported as an SAE (see [Section 6.1.1](#) for reporting details.).

6.6 Potential Drug Induced Liver Injury (DILI)

Wherever possible, timely confirmation of initial liver-related laboratory abnormalities should occur prior to the reporting of a potential DILI event. All occurrences of potential DILIs, meeting the defined criteria, must be reported as SAEs (see [Section 6.1.1](#) for reporting details).

Potential drug induced liver injury is defined when all three of the following are present:

- 1) Aminotransaminase (AT, ALT or AST) elevation > 3 times upper limit of normal (ULN)
- 2) Total bilirubin > 2 times ULN, without initial findings of cholestasis (elevated serum alkaline phosphatase),
- 3) No other immediately apparent possible causes of AT elevation and hyperbilirubinemia, including, but not limited to, viral hepatitis, pre-existing chronic or acute liver disease, or the administration of other drug(s) known to be hepatotoxic.

6.7 Other Safety Considerations

Any significant worsening noted during interim or final physical examinations, electrocardiogram, x-ray filming, any other potential safety assessment required or not required by protocol should also be recorded as a nonserious or serious AE, as appropriate, and reported accordingly.

7 DATA MONITORING COMMITTEE AND OTHER EXTERNAL COMMITTEES

One independent committee will be utilized, a DMC. The DMC will be utilized to provide general oversight and safety considerations for this study, CA209331. The DMC will provide advice to the Sponsor regarding actions the committee deems necessary for the continuing protection of subjects enrolled in this study. The DMC will be charged with assessing such actions in light of an acceptable risk/benefit profile for nivolumab. The DMC will act in an advisory capacity to BMS and will monitor subject safety data for the study.

The DMC will be advisory to the clinical study leadership team. The clinical study leadership will have responsibility for overall conduct of the study including managing the communication of study data. The group will be responsible for promptly reviewing the DMC recommendations, for providing guidance regarding the continuation or termination of the study, and for determining whether amendments to the protocol or changes to the study conduct are required.

Details of the DMC responsibilities and procedures will be specified in the DMC charter.

When required, adjudicated events will be submitted to the DMC and Health Authorities for review on a specified timeframe in accordance with the adjudication documentation.

8 STATISTICAL CONSIDERATIONS

8.1 Sample Size Determination

In this study, the primary endpoint of OS will be evaluated for treatment effect at the overall alpha level of 0.05 (two-sided). Approximately 560 subjects will be randomized at a ratio of 1:1 into two arms: Arm A (nivolumab); Arm B (chemotherapy: topotecan or amrubicin). For sample size calculation, non-proportional hazard model with a piecewise exponential distributions in both arms are assumed. Based on published survival curves for topotecan, a 2-piece exponential distribution with an 8-month median OS and taking into account that a limited number of subjects might receive immuno-oncology as subsequent therapy, a conservative 5% 2-year survival rate is assumed for the control arm. A delayed effect for nivolumab with a hazard ratio (HR) of 1 for the first 8 months and an HR of 0.5 thereafter is assumed. The final analysis will take place 34 months after the first patient have been randomized and no formal interim analysis will be conducted. The 560 subjects are expected to be randomized in 18 months, resulting in about 16 months of follow-up for the last subject randomized at the time of the primary analysis. It is anticipated that approximately 480 events will be observed at the time of the analysis, leading to 90% power to detect a difference in overall survival as tested via a log-rank test with a two-sided 0.05 type I error rate. Power calculations were performed using EAST® Software (version 6.4.1).

The decision to incorporate the China subset into the overall population for analysis is the result of a review of the protocol statistical assumptions in comparison to recent data from the CA209032 study in 2L+ SCLC subjects.²⁸ The data from CA209032, which were not available at the time of protocol design, suggest a delayed effect of nivolumab with a non-proportional hazard for survival. Additionally, review of recently generated real-world data for topotecan resulted in updated assumptions for the control arm. Given the updated statistical assumptions, incorporation of the China subset into the study analyses grants adequate statistical power by increasing the study sample size.

| Table 8.1-1: Sample Size Justification | |
|---|---------------------------------------|
| Primary Endpoint | OS |
| Power | 90% |
| Alpha level | 0.05 |
| Sample size | 560 |
| Accrual duration | 18 months |
| Timing of the analysis from randomization of first subject (months) | 34 |
| Hypothesized OS rate at 8 months | 50% in both arms (HR=1 up to Month 8) |
| Hypothesized OS rate at 24 months | 5% vs 16% (HR=0.5 from Month 8) |
| Expected Average HR | ~0.745 |
| Expected number of event at 34 months | 482 |

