Following platinum-based first-line therapy, about 80% LD-SCLC patients and all of ED SCLC patients have disease progression.⁷ Patients whose response after first-line platinum-based therapy last beyond 180 days are the candidates for rechallenge with platinum doublet therapy. Others are treated with single-agent topotecan, the only approved second-line therapy in the US. Approval was based on a Phase 3 study of single agent intravenous topotecan versus a regimen consisting of cyclophosphamide, doxorubicin, and vincristine (CAV) which showed an improved objective response rate (ORR, 24.3% vs 18.3%, P = 0.285) while median survival was similar between two arms (25 weeks vs 24.7 weeks).⁸ In another Phase 3 trial comparing supportive care alone with supportive care with oral topotecan in patients with relapsed SCLC, the median survival was statistically significantly improved for the topotecan arm (25.9 weeks [95% confidence interval {CI}, 18.3 to 31.6]), compared to supportive care only (13.9 weeks [95% CI, 11.1 to 18.6]).⁹ In a randomized Phase 3 trial of amrubicin versus topotecan as second-line treatment for patients with SCLC, amrubicin did not improve survival when compared with topotecan.¹⁰ For second-line SCLC, the median OS was 6.7 months based on a meta analysis using 21 studies published between 1984 and 2011.¹¹ In summary, there is a high unmet medical need for the treatment of patients with recurrent or relapsed SCLC.

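### Does the 8-month control median make the stated 90% power for overall survival wrong?

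*Protocol*

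**What the plan says.** Protocol 8.1, repeated in the Synopsis and SAP 5, states: "Approximately 560 subjects will be randomized at a ratio of 1:1 into two arms". The control arm is introduced as "Based on published survival curves for topotecan, a 2-piece exponential distribution with an 8-month median OS", and the tail is set by the statement that "a conservative 5% 2-year survival rate is assumed for the control arm". The hazard ratio is 1 up to month 8 and 0.5 afterwards. Accrual takes 18 months and the analysis falls at month 34. Tables 1, 8.1-1 and 5-1 give 50% survival at 8 months in both arms, 5% versus 16% at 24 months, an average hazard ratio of about 0.745 and 482 deaths, "leading to 90% power to detect a difference in overall survival as tested via a log-rank test with a two-sided 0.05 type I error rate".

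Two further statements bear on the inputs. Protocol 8.1 and SAP 5 say that a review of recent real-world topotecan data changed the control-arm assumptions. SAP 5 also says the assumptions were updated from the median survival seen with nivolumab after first-line chemotherapy in CA209032.

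The background in Protocol 1.1.1 reports, for intravenous topotecan against a three-drug regimen, "median survival was similar between two arms (25 weeks vs 24.7 weeks"; for oral topotecan, "the median survival was statistically significantly improved for the topotecan arm (25.9 weeks [95% confidence interval {CI}, 18.3 to 31.6"; and for second-line treatment in general, "the median OS was 6.7 months based on a meta analysis using 21 studies published between 1984 and 2011".

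**The concern.** The sample-size section credits the 8 months to published topotecan curves, yet no published median printed in the protocol reaches 8 months. At 30.4375 days per month, 25 weeks is 5.75 months and 25.9 weeks is 5.96 months. The oral trial's upper confidence limit of 31.6 weeks is 7.27 months.

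The direction looks favourable to the sponsor. With no effect before month 8, only patients alive then can contribute to a difference. The plan has 50% alive; medians of 5.75 to 6.7 months, with constant hazard to month 8, leave 38% to 44%. The 5% two-year rate also raises the control hazard just when benefit is assumed to begin.

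If the shorter medians were the right input and everything else stayed fixed, the chance of missing the hypothesised effect would be 20–35% rather than 10%. A negative result would then be read against an overstated power. PFS and ORR are formally tested only after a significant OS result.

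**Working it through.** **Step 1: rebuild the plan's curves** (inputs from Protocol 8.1 and Table 8.1-1).

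- Control hazard to month 8: ln 2 / 8 = 0.0866 per month.
- Control hazard after month 8: ln(0.50/0.05) / 16 = ln 10 / 16 = 0.1439 per month.
- Nivolumab hazard after month 8: 0.1439 × 0.5 = 0.0720 per month.
- Nivolumab survival at 24 months: 0.5 × √0.1 = 0.158, the tabled 16%.

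**Step 2: reproduce the power.** With 280 per arm, uniform accrual over 18 months and cutoff at month 34, power is Φ(|U|/√V − 1.96), where U and V are the expected log-rank score and its variance.

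- No dropout: 500 deaths, average hazard ratio 0.740, power 91.4% (simulation 91.9%).
- Dropout of about 0.46% per month (an assumption, chosen to give 482 deaths; the plan states none): hazard ratio 0.746, power 88.9% (simulation 89.6%).
- Schoenfeld check with the tabled figures: √482 / 2 × |ln 0.745| − 1.96 = 10.977 × 0.2944 − 1.96 = 1.27, and Φ(1.27) = 89.8%.

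The table is coherent and 90% is right for what it assumes.

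**Step 3: shorten the control median.** The plan puts three things at month 8: the median, the change in control hazard, and the onset of effect. Moving the median forces a decision about the other two and about the nivolumab curve. All rows keep 5% control survival at 24 months and assume no dropout.

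| Control median (months) | (a) Both arms shortened, onset fixed at month 8 | (b) Onset and hazard change move with the median | (c) Planned nivolumab curve kept |
|---|---|---|---|
| 5.75 | 67% | 92% | 99.7% |
| 5.96 | 71% | 92% | 99% |
| 6.7 | 81% | 92% | 98% |

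Column (a) is the source of the alarming range. Because the hazard ratio is 1 to month 8, lowering the control median there also lowers the nivolumab median to 5.75–6.7 months, although SAP 5 says the assumptions were updated from the nivolumab median observed in CA209032. Column (c) respects that anchor; it depends on the 5% tail and would fall if the control tail were higher. In column (b), replacing the 5% tail by a constant control hazard gives 91%, 90% and 87%. The direction of the change is therefore set by the companion assumption, not by the control median alone.

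**Step 4: is 8 months contradicted?** Protocol 1.1.1 prints two topotecan medians, from reports of 1999 and 2006, and one mixed second-line figure covering 1984 to 2011. The documents also cite a Phase 3 trial of amrubicin against topotecan (Protocol 1.1.1) and one of oral against intravenous topotecan (Protocol 1.1.4), and print no survival median for either. The real-world topotecan data are given as a reason for updating the control arm, again without a value. Entry is limited to ECOG 0 or 1, one prior platinum regimen, and at least four cycles or a response (Protocol 3.3.1). One older trial's confidence limit does not bound the control median here.

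**Step 5: the 5% two-year rate.** A constant hazard with an 8-month median would leave 2^(−24/8) = 12.5% alive at 24 months, and power would be 80%. But the documents print no two-year topotecan survival rate to test 5% against. Constant hazard at the printed topotecan medians gives 2^(−24/5.75) = 5.5% and 2^(−24/5.96) = 6.1%, close to the plan; 6.7 months gives 8.3%. One cannot reject the 8-month median and also use it to argue that the tail should be 12.5%.

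**The case for a change.** The strongest reply is that column (a) is the literal reading. The plan fixes the delay at 8 calendar months and gives no reason to tie it to the control median. On that reading every printed median gives less than 90%, and the loss would not show in the death count, which stays at 503–507 against 500. The 8-month sentence credits published curves, not the real-world data, and Protocol 1.1.1 says amrubicin did not improve survival over topotecan, so the amrubicin option gives no documented reason for a longer median.

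Much of this is fair. Column (a) is a legitimate sensitivity scenario, the source of the 8 months is not identified, and the plan shows no power for other control medians. But column (a) still requires the nivolumab median to fall with the control median. Writing power of 80% or 70% into the plan would record one debatable combination of assumptions as if it followed from the control median. The case also needs 8 months to be wrong, and the documents leave that open.

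**Conclusion.** The concern does not hold. Under its stated assumptions the design has the power it claims: 91.4% without dropout, 88.9% with dropout assumed so as to match 482 deaths, and 89.8% from the tabled deaths and average hazard ratio. The disagreement is about an input that the documents neither prove nor disprove. The effect of changing that input runs from about 67% to 99.7% in the table above, depending on whether the month-8 onset and the planned nivolumab curve are kept. Nothing in the documents supports striking out the description of the 5% tail as conservative, because no two-year rate is given for comparison.

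What is left is a missing citation for the 8-month median. Supplying it would alter no test, significance level, sample size, analysis time or result. This conclusion rests on uniform accrual, an unstratified log-rank calculation, and the absence of any printed value for the real-world topotecan data.

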8.2 Populations for Analyses

- All enrolled subjects: All subjects who sign an informed consent form and are registered into the IVRS
- All randomized subjects: All enrolled subjects who are randomized to any treatment arm in the study. This is the primary dataset for analyses of efficacy and baseline characteristics.
- All treated subjects: All enrolled subjects who received at least one dose of nivolumab, or chemotherapy. This is the primary dataset for dosing and safety.
- PK subjects: All enrolled subjects with available serum time-concentration data from randomized subjects dosed with nivolumab.
- All PD-L1 tested subjects: All subjects, randomized or not, who had a tumor biopsy specimen available for PD-L1 expression testing (validated assay). This includes both randomized and screen failure subjects.
- All randomized subjects with quantifiable PD-L1 expression at baseline: Randomized subjects with at least one tumor sample collected at baseline, with number viable tumor cells ≥ 100 , and percentage of viable tumor cells exhibiting PD-L1 membrane staining $\geq 0\%$.
- Tumor Mutational Burden (TMB) evaluable Subjects: All randomized subjects with baseline evaluable TMB

- Biomarker subjects: All treated subjects with biomarker data available.
- China Population: all subjects enrolled in China. Additional analyses exploring the consistency of findings in the China cohort may be conducted. Details of these analyses will be provided in the analysis plan.

8.3 Endpoints

8.3.1 Primary Endpoint(s)

The primary endpoint for the study is OS. It is defined as the time from randomization to the date of death. A subject who has not died will be censored at last known date alive. OS will be followed continuously while subjects are on the study drug and every 3 months via in-person or phone contact after subjects discontinue the study drug.

8.3.2 Secondary Endpoint(s)

Secondary endpoints include ORR and PFS.

8.3.2.1 Progression Free Survival

PFS is defined as the time from randomization to the date of the first documented tumor progression (per RECIST 1.1) or death due to any cause. Subjects who die without a reported prior progression will be considered to have progressed on the date of their death. Subjects who did not progress or die will be censored on the date of their last evaluable tumor assessment. Subjects who did not have any on study tumor assessments and did not die will be censored on the date they were randomized. Subjects who started any subsequent anti-cancer therapy without a prior reported progression will be censored at the last evaluable tumor assessment prior to initiation of the subsequent anti-cancer therapy. Tumor response will be assessed every 6 weeks (± 5 days) (from the first dose of study drug) until Week 30, and every 12 weeks (± 5 days). Tumor assessment will continue until disease progression (or until discontinuation of study drug in subjects receiving nivolumab beyond progression), lost to follow-up, withdrawal of study consent, or the study ends.

8.3.2.2 Objective Response Rate

The ORR will be based on the best overall response on study defined using RECIST 1.1, as assessed by the investigator. ORR is defined as the proportion of all randomized subjects whose BOR from baseline is either a CR or PR per RECIST 1.1 criteria. BOR is determined by the best response between the date of randomization and the date of objectively documented progression or the date of subsequent anti-cancer therapy, whichever occurs first. For subjects without documented progression or subsequent anti-cancer therapy, all available response designations will contribute to the BOR determination. For subjects who continue nivolumab beyond progression, the BOR should be determined based on tumor assessments before initial RECIST 1.1 defined progression. The comparison of ORR will be carried out using a two-sided Cochran-Mantel-Haenszel (CMH) test stratified by the stratification factors as described in [Section 3.1](#) associated odds ratio and 95% CI will be calculated. Rates and their 2-sided exact CI will be calculated by the method of Clopper and Pearson for each randomized arm.

In addition, DOR and TTR will be summarized in each randomized arm. DOR is defined as the time between the date of first confirmed response to the date of the first documented tumor progression (per RECIST 1.1) or death due to any cause. Subjects who neither progress nor die will be censored on the date of their last assessment. TTR is defined as the time from randomization to the date of the first confirmed CR or PR. DOR and TTR will be evaluated for responders (confirmed CR or PR) only.

8.3.3 Exploratory Endpoint(s)

PD-L1 expression is defined as the percent of tumor cells demonstrating plasma membrane PD-L1 staining of any intensity using an IHC assay.

Safety and tolerability objective will be measured by the incidence of AEs, serious adverse events, deaths, and laboratory abnormalities.

Adverse event assessments and laboratory tests are performed at baseline, and continuously throughout the study at the beginning of each subsequent cycle.

Tumor Mutational Burden (TMB) is measured using FoundationOne CDx™ (F1CDx) assay, a comprehensive genomic profile (CGP) assay based on baseline tumor tissue. TMB is defined as the number of somatic, coding, base substitution, and indel mutations per megabase of genome examined. All base substitutions and indels present at 5% allele frequency or greater in the coding region of targeted genes, including synonymous alterations, are initially counted before filtering as described below. Synonymous mutations are counted in order to reduce sampling noise. While synonymous mutations are not likely to be directly involved in creating immunogenicity, their presence is a signal of mutational processes that will also have resulted in nonsynonymous mutations and neoantigens elsewhere in the genome. Non-coding alterations were not counted. Alterations listed as known somatic alterations in COSMIC and truncations in tumor suppressor genes were not counted, since our assay genes are biased toward genes with functional mutations in cancer.

Alterations predicted to be germline by the somatic-germline-zygosity algorithm were not counted. Alterations that were recurrently predicted to be germline in our cohort of clinical specimens were not counted. Known germline alterations in dbSNP were not counted. Germline alterations occurring with two or more counts in the ExAC database were not counted.

To calculate the TMB per megabase, the total number of mutations counted is divided by the size of the coding region of the targeted territory.

Definition of high tumor mutational burden: high TMB will be provided in Statistical Analysis Plan.

Time to Symptom deterioration (TTSD) is defined as the time between the date of randomization and the first date of a 10 point or more increase from baseline in the LCSS Average Symptom Burden Index (ASBI). Subjects who did not meet the criteria of a 10 points or more increase from baseline in LCSS ASBI will be censored on their last LCSS assessment date. Subjects who did not have any on study LCSS assessment will be censored on their date of randomization.

The **LCSS** is a measure of disease-related symptoms and quality of life suited to use in patients suffering from lung cancer. It includes six items measuring loss of appetite, fatigue, coughing, shortness of breath, hemoptysis, and pain. Three additional items measure overall symptom burden, disease-related functional limitations, and quality of life. The questionnaire uses a 24 hour recall period, and responses for each item are captured using a 100-mm visual analog scale (VAS). Scores for individual items ranging from 0 (no symptomatology or highest quality of life) to 100 (worst symptomatology or quality of life) are derived by dividing the length of the line drawn from the lowest possible response to the patient's response by the length of the VAS and multiplying the resulting quotient by 100.

An average symptom burden index (ASBI) score can be derived as the average of scores for the six symptom-related items with a clinically meaningful change in ASBI score being defined as 10 points.

Disease-related symptom deterioration rate by Week 12 and by Week 24 is defined as the proportion of randomized subjects who had 10 points or more increase from baseline in ABSI score at any time between randomization and Week 12/Week 24, respectively.

Subjects' overall health status will be assessed using The EuroQol Group's self-reported health status measure (**EQ-5D**). EQ-5D essentially has 2 health status components - the EQ-5D descriptive system and the EQ visual analogue scale (EQ VAS). The EQ-5D descriptive system comprises the following 5 dimensions: mobility, self-care, usual activities, pain/discomfort and anxiety/depression. Each dimension has 3 levels: no problems, some problems, severe problems. The EQ VAS records the subject's self-rated health state on a 100-point vertical, visual analogue scale (0 = worst imaginable health state; 100 = best imaginable health state).²⁹

Serum concentrations will be used to characterize the PK of nivolumab using a population PK approach and to explore exposure-safety and exposure-efficacy relationships.

Other exploratory endpoints for pharmacogenomics, immunogenicity and outcomes research are discussed in detail in [Sections 8.4.5](#) through [8.4.7](#).

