7.9.1 LCSS questionnaire

LCSS questionnaire completion rate, defined as the proportion of questionnaires actually received out of the expected number (i.e., the number of subjects still on treatment or in follow-up), will be calculated and summarized at each assessment point.

Baseline and change from baseline of the average symptom burden index score at each assessment point will be summarized using descriptive statistics (N, mean, median, SD, 25th and 75th percentiles) by treatment group, as randomized.

Kaplan-Meier plots for TTD in symptoms as measured by LCSS ASBI would be presented along with median TTD and corresponding 95% CI.

TTD rates at fixed timepoints Week 6, 12 and 24 will be derived from the Kaplan Meier estimate and corresponding confidence interval will be derived based on Greenwood formula¹⁸ for variance derivation and on log-log transformation applied on the survivor function $S(t)$ ¹⁹.

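### The Week 12/24 symptom-deterioration rate scores deaths and missing questionnaires as not deteriorated, so an arm with more early deaths can look better on it

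*Protocol*

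**What the plan says.** Protocol 8.3.3 defines two symptom endpoints from the ASBI.

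- **TTSD.** The event is the first rise of at least 10 points from baseline, and death is not part of it. "Subjects who did not meet the criteria of a 10 points or more increase from baseline in LCSS ASBI will be censored" at the last LCSS date. In addition, "Subjects who did not have any on study LCSS assessment will be censored on their date of randomization", so a death before the first on-study questionnaire contributes no follow-up time.
- **Week 12 and Week 24 deterioration rate.** This is "the proportion of randomized subjects who had 10 points or more increase from baseline in ABSI score at any time between randomization" and the week in question. The denominator is everyone randomized; the numerator is observed rises only.

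Protocol 8.4.6 specifies no analysis of that proportion. SAP 7.9.1 gives Kaplan-Meier plots and medians instead, and "TTD rates at fixed timepoints Week 6, 12 and 24 will be derived from the Kaplan Meier estimate". The visible SAP text does not define TTD, has no death rule for it, and plans no test between arms.

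PFS is handled differently. In Protocol 8.3.2.1, "Subjects who die without a reported prior progression will be considered to have progressed on the date of their death".

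Under Table 5.1-4, LCSS collection ends at Follow-up Visit 2; the survival visits collect EQ-5D only.

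**The concern.** A subject who dies in Week 8 without a recorded 10-point rise is scored, under the Protocol's rate, the same as a subject who is alive at Week 24 with stable symptoms. The same applies to a living subject who stops returning questionnaires. In relapsed SCLC many subjects die inside a 24-week window, so this is not a rare case.

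The Protocol objective for TTSD compares nivolumab with chemotherapy. If one arm has more early deaths, the Week 12/24 rate moves in that arm's favour with no difference in symptoms, and a reader could take the result as symptom benefit. For TTSD the question is whether censoring deaths at the last LCSS causes a similar shift. That depends on how death and deterioration are related.

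**Working it through.** **The plan's own figures first.** The documents state no figure for the symptom endpoints, so the check starts from the survival assumptions in Protocol Table 8.1-1.

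- Death hazard to Month 8 (50% alive at 8 months): ln 2 / 8 = 0.0866 per month.
- Control hazard after Month 8: ln(0.50/0.05)/16 = 0.1439. Half of it for nivolumab is 0.0720. Survival at 24 months is then 5% and 0.5 × exp(−0.0720 × 16) = 15.8%, against the stated 5% and 16%.
- Power at 482 events and hazard ratio 0.745: Φ(√482/2 × |ln 0.745| − 1.96) = Φ(1.27) = 89.8%, against the stated 90%.

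**Deaths in the window.** With 30.4375 days per month (SAP 8), Week 12 is 2.76 months and Week 24 is 5.52 months.

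- Week 12: 1 − exp(−0.0866 × 2.76) = 21.3%, about 60 of 280 per arm.
- Week 24: 1 − exp(−0.0866 × 5.52) = 38.0%, about 106 of 280 per arm.

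Not all of these are misclassified, because a death after a recorded rise is counted correctly. With an assumed deterioration hazard L = 0.1 per month and M = 0.0866, deaths before deterioration by Week 24 are M/(L+M) × [1 − exp(−(L+M) × 5.52)] = 0.464 × 64.3% = about 30%.

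**The Protocol proportion.** Assumptions not in the documents: underlying deterioration by Week 24 is identical in both arms (40%, range 30–50%), it is independent of death, and one arm has 1.5 times the early death hazard (0.130 per month).

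- Proportion = L/(L+M) × [1 − exp(−(L+M)t)], where L = −ln(1 − underlying)/5.52; for 40%, L = 0.0926.
- Lower-mortality arm: 0.0926/0.1792 × 62.8% = 32.4%.
- Higher-mortality arm: 0.0926/0.2225 × 70.7% = 29.4%.
- Deterioration or death = 1 − exp(−(L+M)t): 62.8% and 70.7%.

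| Underlying, Week 24 | Proportion, higher vs lower mortality | Deterioration or death, higher vs lower |
|---|---|---|
| 30% | 21.9% vs 24.2% | 65.8% vs 56.6% |
| 40% | 29.4% vs 32.4% | 70.7% vs 62.8% |
| 50% | 37.2% vs 40.8% | 75.6% vs 69.0% |

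At 1.25 times the early death hazard and 40% underlying, the proportion is 30.9% vs 32.4%. At equal mortality it is 32.4% in both arms.

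**TTSD by Kaplan-Meier.** A simulation used 40% underlying deterioration, 1.5 times the early death hazard, LCSS every 3 weeks in both arms, and a Gaussian copula linking deterioration and death. The correlations are assumed.

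| Correlation | KM rate at Week 24, higher vs lower mortality | Deterioration or death, higher vs lower |
|---|---|---|
| 0 | 40.0% vs 40.0% (to rounding) | 70.7% vs 62.8% (closed form) |
| 0.5 | 30.2% vs 32.9% | 62.7% vs 55.0% |
| 0.8 | 21.3% vs 27.4% | 56.7% vs 48.8% |

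With no link, censoring deaths does not move the comparison. With a positive link and unequal mortality, Kaplan-Meier also favours the arm with more deaths. Counting death as an event reverses the direction in every row.

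**Missing questionnaires.** Follow-up Visit 2 falls 35 + 80 = 115 days (16.4 weeks) after the last dose, before visit windows. A subject whose last dose is before about Week 7.6 (24 − 16.4) therefore has no scheduled LCSS at Week 24, even if alive.

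**The case against.** The strongest case against has four parts.

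1. **The plan assumes a hazard ratio of 1 to Month 8**, which covers both time points. This stands: under that assumption deaths create no distortion between arms. A reader might infer that the plan builds in a bias towards one arm. It does not; the effect needs early mortality to differ in fact.
2. **The SAP does not report the crude proportion.** This also stands. SAP 7.9.1 uses Kaplan-Meier rates, so the scoring problem sits in the Protocol definition and the two documents disagree on what the Week 12/24 rate is. A reader might also conclude that the SAP has no rule for death anywhere. That goes too far: its exploratory text is partly redacted, so such a rule cannot be excluded.
3. **Censoring deaths in TTSD is a recognisable choice and need not mislead.** Partly right. A reader might infer that TTSD favours the higher-mortality arm as mechanically as the proportion does. It does not: with independent deterioration and death the Kaplan-Meier rates are equal. A positive link is plausible in this disease, but its strength is not in the documents.
4. **The endpoints are exploratory and OS by arm is reported anyway.** True, and this sets the priority. It does not make a death a good symptom outcome.

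A tempting stronger remedy is to replace Kaplan-Meier by the cumulative incidence of deterioration with death as a competing event. That would not help by itself. It is the same formula that produced 29.4% against 32.4% above, and it falls as deaths rise.

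**Conclusion.** The point holds for the Protocol's Week 12/24 rate. As defined, it counts deaths and missing questionnaires without a recorded rise as not deteriorated. About 21% of subjects are expected dead by Week 12 and 38% by Week 24. About 30% would die before deterioration by Week 24 at an assumed deterioration hazard of 0.1 per month.

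The effect between arms is conditional. With 1.5 times the early mortality and identical underlying deterioration, the worse-surviving arm looks about 2 to 4 points better at Week 24. With equal early mortality, deaths cause no difference. For TTSD a shift needs both unequal early mortality and a positive link between death and deterioration; it is then 2.7 points at correlation 0.5 and 6.1 points at 0.8. The mortality ratio, underlying deterioration and correlations are all assumptions.

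OS, alpha, sample size and the PFS/ORR hierarchy are unaffected. This is a low-priority, cheap improvement.

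**What to change.** 1. **Week 12 and Week 24.** By arm, over all randomized subjects, report four categories: deteriorated; died without recorded deterioration; missing (alive, no recorded rise, no LCSS covering the time point); alive and not deteriorated. Use this in place of a single rate that puts the second and third categories into the fourth.
2. **SAP 7.9.1.** Keep the Kaplan-Meier analysis of TTSD, state that deaths are censored at the last LCSS, and add time to deterioration or death by arm beside it, with rates at Weeks 6, 12 and 24. Do not substitute the cumulative incidence of deterioration alone.
3. **Reconcile the documents.** Make Protocol 8.3.3 and SAP 7.9.1 agree on what the Week 12/24 rate is, and define TTD in the SAP. If the redacted SAP text already holds a death rule, cite it in 7.9.1.

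Cost: SAP wording, one extra exploratory table and one extra curve, from LCSS and survival data already collected. The presentation becomes slightly longer.
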